10.1.4.2 Evaluation of Non-Target Lesions

Complete Response (CR): Disappearance of all non-target lesions and normalization of tumor marker level.

Note: If tumor markers are initially above the upper normal limit, they must normalize for a subject to be considered in complete clinical response

Incomplete Response/Stable Disease (SD): Persistence of one or more non-target lesions and/or maintenance of tumor marker level above the normal limits.

Progressive Disease (PD): Appearance of one or more new lesions (new lesions must be $>$ slice thickness) and/or unequivocal progression of existing non-target lesions.

Unknown (UN): Assessment of target lesions cannot be made due to insufficient or unevaluable data. In this case, a concise explanation must be given.

Note: Although a clear progression of "non-target" lesions only is exceptional, in such circumstances, the opinion of the treating physician should prevail and the progression status should be confirmed at a later time by review of the Principal Investigator (or Protocol Chair). Additionally, the cytological confirmation of the neoplastic origin of any effusion that appears or worsens during treatment is mandatory to differentiate between stable or progressive disease status.

10.1.4.3 Evaluation of Best Overall Response

The best overall response is the best response recorded from the start of the treatment until disease progression/recurrence (taking as reference for progressive disease the smallest measurements recorded since the treatment started). The participant's best response assignment will depend on the achievement of both measurement and confirmation criteria.

Target Lesions	Non-Target Lesions	New Lesions	Overall Response	Best Response for this Category Also Requires:
CR	CR	No	CR	≥ 4 wks confirmation
CR	Non-CR/Non-PD	No	PR	≥ 4 wks confirmation
PR	Non-PD	No	PR	
SD	Non-PD	No	SD	Documented at least once ≥ 4 wks from baseline
PD	Any	Yes or No	PD	No prior SD, PR or CR
Any	PD*	Yes or No	PD	
Any	Any	Yes	PD	

* In exceptional circumstances, unequivocal progression in non-target lesions may be accepted as disease progression.

Note: Participants with a global deterioration of health status requiring discontinuation of treatment without objective evidence of disease progression at that time should be reported as "*symptomatic deterioration*". Every effort should be made to document the objective progression even after discontinuation of treatment.

10.1.5 Duration of Response

Duration of overall response: The duration of overall response is measured from the time measurement criteria are met for CR or PR (whichever is first recorded) until the first date that recurrence or PD is objectively documented, taking as reference for PD the smallest measurements recorded since the treatment started.

Duration of overall complete response: The duration of overall CR is measured from the time measurement criteria are first met for CR until the first date that recurrent disease is objectively documented.

Duration of stable disease: Stable disease is measured from the start of the treatment until the criteria for progression are met, taking as reference the smallest measurements recorded since the treatment started.

10.1.6 Progression-Free Survival

Progression-Free Survival (PFS) is defined as the duration of time from start of treatment to time of objective disease progression or death, or is censored at the time of last disease evaluation.

11. ADVERSE EVENT REPORTING REQUIREMENTS

11.1 General

Adverse event collection and reporting is a routine part of every clinical trial. This study will use the descriptions and grading scales found in the NCI Common Terminology Criteria for Adverse Events version 4.0 (CTCAE v4.0) that is available at <http://ctep.cancer.gov/reporting/ctc.html>.

Information on all adverse events, whether reported by the participant, directly observed, or detected by physical examination, laboratory test or other means, will be collected, recorded, followed and reported as described in the following sections.

Adverse events experienced by participants will be collected and reported from initiation of study medication, throughout the study, and within 30 days (or 5 half-lives, whichever is longer) of the last dose of study medication. Participants who experience an ongoing adverse event or related to a study procedures and/or study medication beyond 30 days will continue to be contacted by a member of the study team until the event is resolved, stabilized, or determined to be irreversible by the participating investigator.

Participants should be instructed to report any serious post-study event(s) that might reasonably be related to participation in this study. The investigator should notify the IRB and any other applicable regulatory agency of any unanticipated death or adverse event occurring after a participant has discontinued or terminated study participation that may reasonably be related to the study.

11.2 Definitions

11.2.1 Adverse Event (AE)

An adverse event is any undesirable sign, symptom or medical condition or experience that develops or worsens in severity after starting the first dose of study treatment or any procedure specified in the protocol, even if the event is not considered to be related to the study.

Abnormal laboratory values or diagnostic test results constitute adverse events only if they induce clinical signs or symptoms or require treatment or further diagnostic tests.

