Nine patients were enrolled in the phase I portion of this study. Two patients on dose level 0 (pazopanib 600 mg daily and everolimus 5 mg daily) experienced dose limiting toxicities (grade 3 rash and pruritus and grade 3 thrombocytopenia requiring a dose reduction). Therefore, three patients were treated at dose level -1 per protocol. None of these three patients experienced a protocol-defined dose-limiting toxicity. Therefore, another three patients were treated at dose level -1 (pazopanib 400 mg daily and everolimus 5 mg daily) without any dose-limiting toxicities. Therefore, per protocol, dose level -1 was defined as the maximum tolerated dose.

Toxicity	Maximum Grade			
	G1	G2	G3	G4
Febrile neutropenia	-	-	1	-
Neutropenia	1	-	-	-
Thrombocytopenia	3	1	1	-

Hematologic toxicities (see table above) included febrile neutropenia (11%), neutropenia (11%), thrombocytopenia (56%), and anemia (36%). Grade 3 febrile neutropenia and thrombocytopenia each occurred in 1 patient. Non-hematologic toxicities were varied, though many were expected based on the known toxicities of everolimus and pazopanib. One patient did experience a grade 3 pneumothorax, which was possibly related to study therapy. Other non-hematologic toxicities included anorexia (11%), bone pain (11%), diarrhea (22%, 11% G3), fatigue (56%), dysgeusia (11%), headache (11%), hypertension (22%), mucositis (33%), musculoskeletal (muscle stiffness after prolonged periods of sitting, 11%), nausea (44%), palmo-plantar erythrodysesthesia syndrome (11%), pneumonia (11% G3), pruritus (11% G3), rash (33%, 11% G3), vomiting (33%), and weight loss (11%). Toxicities noted in laboratory evaluations were generally consistent with what is expected with both agents administered separately. G3 and 4 laboratory toxicities included increased ALT, hypophosphatemia, and hypouricemia each in 1 patient, and increased lipase in 2 patients.

Treatment was generally well tolerated at the MTD. Two of 6 patients came off treatment after 2 cycles because of toxicity. The others stopped treatment due to disease progression or physician decision.

Antitumor activity

Encouraging antitumor activity was noted in the bladder cancer patients treated on pazopanib and everolimus. Of five urothelial cancer patients evaluable, 3 had stable disease for 4 months, 4 months and 5.5 months respectively. One patient had a complete response which lasted 14 months.

Tumor type	(n)	Best objective response

Bladder	5	3 SD, 1CR, 1 NE

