Grade 3 or 4 Thrombocytopenia (platelets $<50 \times 10^9/L$)	
Interrupt pazopanib and everolimus until recovery to grade \leq 1 ($\geq 75 \times 10^9/L$). Then resume pazopanib and everolimus at one dose level lower. If grade 3 or 4 thrombocytopenia recurs, discontinue pazopanib and everolimus.

Grade 1 & 2 Neutropenia (neutrophils $\geq 1 \times 10^9/L$)	
Grade 3 Neutropenia (neutrophils $<1, \geq 0.5 \times 10^9/L$)	
No modification of dose.

	
Interrupt everolimus and Pazopanib until resolution to grade ≤ 1 or baseline value
 
If AE resolution occurs ≤ 7 days, reintroduce everolimus and pazopanib at the same dose level.
 
If AE resolution occurs > 7 days (within 28 days), reintroduce everolimus and pazopanib at one dose level lower, if available. Discontinue patient from study therapy if recurrent grade 3 or greater neutropenia after two dose reductions.

Grade 4 Neutropenia (neutrophils $< 0.5 \times 10^9/L$)
	
Interrupt pazopanib and everolimus until recovery to grade ≤ 1 (neutrophils $\geq 1.5 \times 10^9/L$). Then resume pazopanib and everolimus at one lower dose level. If grade 3 or grade 4 neutropenia occurs despite two dose reductions, discontinue pazopanib and everolimus.

Grade 3 febrile neutropenia (not life-threatening)
	
Hold further pazopanib and everolimus until the ANC $\geq 1,500/\text{mm}^3$ and fever has resolved and antibiotics are discontinued. Then resume pazopanib and everolimus at one dose level lower. If febrile neutropenia recurs, discontinue pazopanib and everolimus.

Grade 4 febrile neutropenia (life-threatening)
	
Discontinue pazopanib and everolimus.

Any hematological or non-hematological toxicity requiring interruption for ≥ 4 weeks
	
Discontinue pazopanib and everolimus

6.3.2 Management of hypertension, proteinuria, hemorrhage/bleeding, venous and arterial thrombosis, QTc prolongation

AE Terms & Descriptions	Dose Modification Algorithms

Hypertension
	

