11.5.2 Non-Serious Adverse Event Reporting Requirements

Non-serious adverse events will be reported to the Principal Investigator (or Protocol Chair) on the toxicity Case Report Forms.

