All patients who receive treatment will be included in toxicity analyses. A summary of the incidence of all treatment-related grade 3-5 toxicities will be provided as maximum grade by toxicity type and body system. Any other information collected (e.g. severity or relatedness to study medication) will be listed as appropriate. Overall maximum grade 3 or higher treatment-related toxicity rates in all treated patients will be calculated. The table below shows the 90% confidence intervals for 0, 2, 4, and 6 patients with grade 3 or higher toxicity in a total of 29 treated patients.

Observed Number of Patients with Grade \geq 3 Toxicity	Grade \geq 3 Toxicity Rate	90% Confidence Interval for True but Unknown Grade \geq 3 Toxicity Rate
0	0.0%	(0.0%, 9.8%)
2	6.9%	(1.3%, 20.2%)
4	13.8%	(4.9%, 28.9%)
6	20.7%	(9.4%, 36.8%)

Exploratory

Relevant somatic and germline alterations will be identified by adaptation and modification of discovery-oriented algorithms in common use at the Broad Institute and MSKCC. We will also apply a series of computational algorithms that predict neutral, detrimental or activating variants. Upon completion, we will deliver a list of somatic and germline variants that perturb cancer genes and associated cellular pathways, associated with response to therapy in this cohort. Relevant associations between mutation status and treatment outcome will be assessed on an exploratory basis, and relevant targeted sequencing may be performed in non-responders to further understand the association between response to study therapy and somatic alterations.

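### The AE definition does not make grade ≥3 or a dose action a trigger for laboratory values, and 14.4 commits only to a treatment-related rate, so the expansion cohort may understate all-cause grade ≥3 toxicity

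*Combined protocol and SAP*

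**What the plan says.** **Definition.** Section 11.2.1 collects adverse events irrespective of cause ("even if the event is not considered to be related to the study") but restricts laboratory findings: "Abnormal laboratory values or diagnostic test results constitute adverse events only if they induce clinical signs or symptoms or require treatment or further diagnostic tests". There are thus three ways in: clinical signs or symptoms, treatment, or further tests.

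**Recording.** Section 11.1 covers events "detected by physical examination, laboratory test or other means, will be collected, recorded, followed and reported". Under 11.3 all adverse events go on case report forms, and under 11.5.2 "Non-serious adverse events will be reported to the Principal Investigator (or Protocol Chair) on the toxicity Case Report Forms".

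**Dose rules.** Section 6.3.1 interrupts both drugs for grade 3 and grade 4 neutropenia and for grade 3-4 thrombocytopenia. For the last it adds: "If grade 3 or 4 thrombocytopenia recurs, discontinue pazopanib and everolimus".

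**Analysis, expansion cohort (14.4).** "A summary of the incidence of all treatment-related grade 3-5 toxicities will be provided as maximum grade by toxicity type and body system", and "Overall maximum grade 3 or higher treatment-related toxicity rates in all treated patients will be calculated". Other information is to be listed where appropriate.

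**Analysis, Phase I (14.1).** The summary covers patients with any adverse event, by dose cohort and without a relatedness limit, together with counts of laboratory values outside set ranges.

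**Phase I experience (2.3).** "G3 and 4 laboratory toxicities included increased ALT, hypophosphatemia, and hypouricemia each in 1 patient, and increased lipase in 2 patients".

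**The concern.** A laboratory event serious enough to interrupt or end treatment is one that a reader would expect to find in the toxicity table. Under 11.2.1 its severity grade and its effect on dosing do not decide whether it is an adverse event. Sites that follow the definition literally could leave such events off the forms, while sites that follow the language of section 6.3 would record them.

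The second issue is the reported quantity. Without a control arm, attribution is the investigator's judgement, and 14.4 promises no rate free of that judgement. Safety is a secondary objective in 1.3.2, and the expansion-cohort text of 14.1 places it in the primary objective. At stake are the completeness of the grade ≥3 rate and whether it can be set beside the Phase I safety data at the same dose.

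**Working it through.** **1. The plan's own figures.** Section 14.4 gives 90% intervals for 29 treated patients. The exact (Clopper-Pearson) limits are: lower = 5th percentile of Beta(x, 29 − x + 1); upper = 95th percentile of Beta(x + 1, 29 − x).

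| x | Rate | Stated | Recomputed |
|---|---|---|---|
| 0 | 0.0% | 0.0-9.8% | 0.0-9.8% |
| 2 | 6.9% | 1.3-20.2% | 1.2-20.2% |
| 4 | 13.8% | 4.9-28.9% | 4.9-28.8% |
| 6 | 20.7% | 9.4-36.8% | 9.4-36.8% |

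All agree within 0.1 point. The table is sound; the question is what enters x.

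**2. Definition against dose rules.** For events without symptoms or treatment:

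| Event | Action in section 6.3 | Status under 11.2.1 |
|---|---|---|
| Grade 3 or 4 neutropenia | Both drugs interrupted; row names no treatment or test | Not clearly an AE, though the grade 3 row speaks of AE resolution |
| Grade 3-4 thrombocytopenia | Both interrupted, stopped on recurrence; row names no treatment or test | Not clearly an AE |
| Grade 4 amylase/lipase | Therapy held; GI consultation recommended | Arguable |
| 24-hour urine protein ≥3 g | Both interrupted; weekly retest | Arguable (retest) |
| ALT >8 × ULN, no bilirubin rise | Both interrupted; serology and liver imaging required | AE, by the further-tests route |

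The clearest gap is in the cytopenias.

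**3. Analysis by cohort.** Phase I (14.1): any AE, plus out-of-range laboratory values. Expansion (14.4): treatment-related grade 3-5 only. An all-cause rate must be at least as high as a treatment-related one, so the two summaries do not measure the same thing.

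**4. Size.** One patient whose only grade ≥3 event is not counted changes the rate by 1/29 = 3.4 points. The number of such patients is not in the documents. As an illustration only, with 1, 2 or 4 uncounted patients assumed:

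| Counted | +1 | +2 | +4 |
|---|---|---|---|
| 4/29 = 13.8% (4.9-28.8) | 5/29 = 17.2% (7.0-32.9) | 6/29 = 20.7% (9.4-36.8) | 8/29 = 27.6% (14.5-44.3) |
| 6/29 = 20.7% (9.4-36.8) | 7/29 = 24.1% (11.9-40.6) | 8/29 = 27.6% (14.5-44.3) | 10/29 = 34.5% (20.0-51.4) |

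**5. How common the events might be.** Section 6.1.2 gives pazopanib-alone grade 3-4 rates. If they carried over to the combination (an assumption):

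- Platelets, 3%: 29 × 0.03 = 0.87 patients expected; chance of at least one = 1 − 0.97^29 = 0.59.
- Neutrophils, below 1%: fewer than 29 × 0.01 = 0.29 expected.
- Lipase, 9%: 29 × 0.09 = 2.61 expected; chance of at least one = 1 − 0.91^29 = 0.94.

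Section 6.1.1 gives grade 3 rates for everolimus in heavily pretreated lymphoma of 16% (neutrophils) and 30% (platelets), which would be 29 × 0.16 = 4.64 and 29 × 0.30 = 8.7. That is a different disease, so these only mark how wide the range is. Under either assumption the figures are ceilings on what could be lost, because only events without symptoms, treatment or further tests are at issue.

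**The case against.** The opposing case has real force.

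- **The further-tests route is wide.** It covers ALT >8 × ULN outright. It may cover the cytopenias too: the grade 3 neutropenia rule turns on recovery within 7 days, but scheduled counts are on days 1 and 15 in cycles 1-2 and once per 28-day cycle after that, so an extra count is needed. A reader might infer that 11.2.1 excludes every laboratory value without symptoms or treatment; it does not. Whether a repeat count to follow recovery is a diagnostic test is open, and sites could decide differently.
- **The protocol elsewhere calls these events AEs.** The grade 3 neutropenia row does so. Another row in 6.3.1 exempts glucose and lipid findings from its grade 3 AE rule, and 6.3.3 introduces the liver table in terms of AEs. This shows the likely intent, and also that 11.2.1 does not match it.
- **Phase I did report laboratory toxicities.** CTCAE evaluation is required at visits, and 14.4 speaks of toxicities rather than adverse events. A reader might infer that the rate is in fact undercounted; no document shows a missed event. But no section requires a graded value that fails 11.2.1 to be recorded as an AE.
- **A treatment-related rate is a legitimate quantity.** Leaving out unrelated events does not undercount it. The weakness is only that no all-cause rate stands beside it. Non-comparability is likewise a possibility, since 2.3 does not state whether its Phase I counts are all-cause.
- **Phase I counts do not measure the loss.** A reader might treat the five grade 3-4 laboratory findings and one grade 3 thrombocytopenia among nine patients as the share that would be missed. They were reported, may overlap in patients, and are not described as asymptomatic or untreated.

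**Conclusion.** The point holds in limited form. Section 11.2.1 lists neither grade ≥3 nor a study-drug action as a trigger, which is out of step with section 6.3; the exposure is clearest for asymptomatic, untreated grade 3-4 cytopenias. Section 14.4 commits to no all-cause grade ≥3 rate in a single-arm cohort. Together these mean that the expansion result may understate all-cause grade ≥3 toxicity and may not be comparable with Phase I.

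The size is 3.4 points per missed patient out of 29; the number of patients is unknown. The conclusion assumes a literal reading of 11.2.1 in which a dose hold, or a repeat count taken only to follow recovery, does not qualify. If sites read it more broadly, the recording gap shrinks or closes, but the absence of an all-cause rate remains. The response endpoint is unaffected. This is an inexpensive correction worth making, and no evidence of error in data already reported.

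**What to change.** In 11.2.1, add that a laboratory value is also recorded as an adverse event if it is CTCAE grade 3 or higher, or if it leads to interruption, reduction or discontinuation of either study drug. This brings the definition into line with section 6.3.

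In 14.4, add an all-cause grade 3-5 table and an all-cause grade ≥3 rate with its 90% interval, beside the treatment-related ones.

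The laboratory tests are already scheduled, AEs are already collected whatever their cause, and no dosing rule changes. The cost is one sentence, one table and one rate, more AE entries for sites, and possibly a less favourable stated toxicity rate.

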11.2.2 Serious adverse event (SAE)

A serious adverse event is an undesirable sign, symptom, or medical condition which:

- is fatal or life-threatening;
- requires or prolongs inpatient hospitalization;

- results in persistent or significant disability/incapacity;
- constitutes a congenital anomaly or birth defect; or
- jeopardizes the participant and requires medical or surgical intervention to prevent one of the outcomes listed above.

Events **not** considered to be serious adverse events are hospitalizations for:

- routine treatment or monitoring of the studied indication, not associated with any deterioration in condition, or for elective procedures
- elective or pre-planned treatment for a pre-existing condition that did not worsen
- emergency outpatient treatment for an event not fulfilling the serious criteria outlined above and not resulting in inpatient admission
- respite care and social reasons in the absence of any deterioration in the patient's general condition

11.2.3 Expectedness

Adverse events can be 'Expected' or 'Unexpected.'

11.2.3.1 Expected adverse event

Expected adverse events are those that have been previously identified as resulting from administration of the agent. For the purposes of this study, an adverse event is considered expected when it appears in the current adverse event list, the Investigator's Brochure, the package insert or is included in the informed consent document as a potential risk.

Refer to Section 6.1 for a listing of expected adverse events associated with the study agent(s).

11.2.3.2. Unexpected adverse event

For the purposes of this study, an adverse event is considered unexpected when it varies in nature, intensity or frequency from information provided in the current adverse event list, the Investigator's Brochure, the package insert or when it is not included in the informed consent document as a potential risk.

11.2.4 Attribution

Attribution is the relationship between an adverse event or serious adverse event and the study treatment. Attribution will be assigned as follows:

- Definite – The AE is clearly related to the study treatment.
- Probable – The AE is likely related to the study treatment.

- Possible – The AE may be related to the study treatment.
- Unlikely - The AE is doubtfully related to the study treatment.
- Unrelated - The AE is clearly NOT related to the study treatment.

11.3 Recording Adverse Events

Adverse event information will be obtained at each contact with the participant. All adverse events will be recorded on the appropriate study-specific case report forms (CRFs).

11.4 Reporting Adverse Events

Each adverse event will be assessed to determine if it meets the criteria for serious adverse event. If a serious adverse event occurs, expedited reporting will follow local policies, and federal guidelines and regulations as appropriate.

It is the responsibility of the participating investigator to notify the Principal Investigator (or Protocol Chair), IRB, and others of all serious adverse events as required in the protocol.

The Principal Investigator (or Protocol Chair) will provide information with respect to adverse events and safe use of the study treatment (e.g., safety reports, Action Letters) to all participating investigators as soon as the information becomes available.

All SAEs, regardless of “expectedness” or “causality” must be reported to the Principal Investigator (or Protocol Chair), [name], via fax within 24 hours of learning of the event. In the event that the participating investigator does not become aware of the serious adverse event immediately (e.g., participant sought treatment elsewhere), the participating investigator is to report the event within 24 hours after learning of it and document the time of his or her first awareness of the adverse event. All SAEs should be recorded on a MedWatch 3500a form. Please fax all supporting documentation as it becomes available.

The contact information for SAE reporting is as follows:

[name]
Dana-Farber Cancer Institute
[contact]

